13.3 Performing AE Assessment

All observed AEs, regardless of suspected causal relationship to the investigational product, will be reported as described in the following sections.

For all AEs, the investigator must pursue and obtain information adequate to determine the outcome of the AE and to assess whether it meets the criteria for classification as a serious adverse event (SAE) requiring immediate notification to FTH or its designated representative.

13.4 Reporting Period

The investigator shall report all SAEs and AESIs to FTH ([contact]) and Pfizer without undue delay but not later than 24 hours from the time he/she has knowledge of these events. The investigator, where applicable, shall send a follow-up report to the sponsor to allow the sponsor to assess whether the serious adverse event has impact on the benefit-risk balance of the clinical trial. The initial and follow-up reports shall identify the trial subjects only by a subject identification code assigned in the trial, specific for each of them.

For all screened patients, beginning at the time of the signature of the informed consent form and concluding 28 days after the last dose of the assigned study treatment or the investigator/patient decision to discontinue treatment or end of study (whichever occurs later), n-TEAEs, and AEs (both serious and non-serious) should be recorded on the eCRF.

Adverse event monitoring should start when the patient takes the study treatment for first time, and continued for at least 28 days following the last dose of study treatment or the investigator/patient decision to discontinue treatment (whichever occurs later).

AEs Ongoing after the Reporting Period: Any ongoing AE should be followed at least every 4 weeks, until they resolve to baseline, stabilize, or are considered to be chronic/irreversible.

SAEs starting after End of Study: SAEs occurring to a patient after the participation of that patient has ended should be reported to the sponsor if the investigator becomes aware of them. The investigator does not need to actively monitor subjects for AEs once the trial has ended.

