9.3 Second Therapy

9.3.1 Group 1: The first 10 patients

Only for the first ten patients included in the study, atezolizumab will be introduced at a dose of 840 mg every two weeks combined with 400 mg/day of bosutinib for 2 cycles (8 weeks). These patients will be closely monitored for safety issues.

If dose-limiting toxicities (DLTs) appear in 2 or more patients the study will end.

A DLT would include either of the following adverse events that occurred during bosutinib therapy in combination with atezolizumab, if it is considered at least possibly related to bosutinib and/or atezolizumab:

- Grade 4 neutropenia (<500/ μ l) persisting for > 7 day duration or Grade 4 white cell count decrease for >7 day duration (<1000/ μ l).
- Febrile neutropenia (ANC<1000/ μ l and fever \geq 38.5°C).

- Grade 4 thrombocytopenia > 48 hour duration or with bleeding requiring platelet transfusion.
- Any Grade 3 or 4 clinically evident non-hematological toxicity.
- Any ≥Grade 3 toxicity that requires >14 days to resolve (to ≤Grade 1 despite optimal medical therapy).

DLTs will be graded according to the NCI CTCAE, v5.0.

If no relevant safety issue, regarding the combination is detected the study will continue.

These initial 10 patients will cross-over from bosutinib 400 mg/day plus atezolizumab 840 mg every 2 weeks to bosutinib 400 mg/day plus atezolizumab 1680 mg every 4 weeks for 10 cycles (40 weeks).

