11.6.1.1 Management of Non-Hematologic Treatment-Related Toxicities

The management of non-hematologic treatment-related toxicities is summarized in Table 1.

Table 1. Non-Hematologic Treatment-Related Toxicities

Adverse Event	Action
Elevated liver transaminases	If elevations in liver transaminases (ALT, AST) $> 5 \times$ institutional upper limit of normal (ULN) occur, bosutinib should be interrupted until recovery to $\leq 2.5 \times$ ULN and may be resumed at 400 mg once daily thereafter. If recovery takes longer than 4 weeks, discontinuation of bosutinib should be considered. If transaminase elevations $\geq 3 \times$ ULN occur concurrently with bilirubin elevations $> 2 \times$ ULN and alkaline phosphatase $< 2 \times$ ULN, bosutinib should be discontinued.
Diarrhea	For Grade 3/4 diarrhea, bosutinib should be interrupted and may be resumed at 400 mg once daily upon recovery to Grade ≤ 1 .
Grade 1	Current dose level

Grade 2	For persistent clinically relevant toxicity ^b not responding to optimal management: Temporarily interrupt treatment, and reintroduce at the same dose or reduce dose by 1 level upon recovery to Grade ≤ 1 within 4 weeks of stopping test article.
Grade 3 ^a	For persistent clinically relevant toxicity ^b not responding to optimal management: Withhold treatment, then dose reduce by 1 level upon recovery to Grade ≤ 1 within 4 weeks of stopping test article. If recovery takes longer than 4 weeks, the Investigator should contact the Sponsor to determine if the patient may continue on treatment.
Grade 4 ^a	Withhold treatment. Investigator and Sponsor to review to determine if patient may continue on treatment with appropriate dose reduction.
	
a. For patients requiring dose reduction due to toxicity, who have been free of the toxicity (Grade ≤ 1) for at least 1 month and are otherwise tolerating study drug, the Investigator may choose to re-escalate dose by 1 dose level back to starting dose.b. Persistent Clinically Relevant Toxicity is defined as - symptoms of toxicity which, despite optimal medical management, persist for ≥ 14 days ("persistent") and cause sufficient symptoms or signs of illness in the subject to warrant further intervention, i.e. dose adjustment ("clinically relevant").

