11.6.2 Dose reduction steps for atezolizumab

Although most immune-mediated adverse events observed with immunomodulatory agents have been mild and self-limiting, such events should be recognized early and treated promptly to avoid potential major complications. Discontinuation of atezolizumab may not have an immediate therapeutic effect and, in severe cases, immune-mediated toxicities may require acute management with topical corticosteroids, systemic corticosteroids, or other immunosuppressive agents.

The investigator should consider the benefit-risk balance a given subject may be experiencing prior to further administration of atezolizumab. Atezolizumab should be permanently discontinued in subjects with life-threatening, immune-mediated adverse events. Specific guidelines for immune-mediated events are provided in Tables 3 to 13.

For all other non-immune mediated adverse events, including infections, atezolizumab should be withheld for Grade 3 or higher toxicity with the following exceptions:

- Grade 3 nausea that responds to antiemetic treatment within 7 days
- Grade 3 vomiting that responds to antiemetic treatment within 7 days
- Grade 3 diarrhea that responds to antidiarrheal treatment within 7 days
- Grade 3 fatigue that was present at baseline or that lasts for <7 days after the last administration of atezolizumab
- Grade 3 asthenia that was present at baseline or that lasts for <7 days after the last administration of atezolizumab

Administration of atezolizumab may be restarted upon recovery from toxicity to Grade 1 or baseline.

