13.9.1 Adverse Event of Special Interest

AESIs require ongoing monitoring by investigators and rapid identification and communication by the investigator to the sponsor. All AESIs, whether they are SAEs or not, must be reported immediately (within 24 hours) to the sponsor. The sponsor has determined that the events listed below (whether considered serious or non-serious by investigators) should be considered AESIs, and should therefore be reported within 24 hours:

- 1) In relation to bosutinib:
 - A. Grade 3-4 diarrhea
 - B. Grade 3-4 nausea and vomiting
 - C. Potential drug-induced liver injury showed by abnormal values in liver enzyme (ALT increased and AST increased) concurrent with abnormal elevation in total bilirubin that meet the criteria outlined below:
 - a. Patients with AST or ALT and total bilirubin baseline values within the normal range who subsequently present with AST or ALT ≥ 3 times the upper limit of normal concurrent with a total bilirubin $\geq 2 \times$ ULN with no evidence of hemolysis and an alkaline phosphatase $\leq 2 \times$ ULN or not available;
 - b. For patients with preexisting ALT or AST or total bilirubin values above the upper limit of normal, the following threshold values should be used:
 - i. For patients with pre-existing AST or ALT baseline values above the normal range: AST or ALT ≥ 2 times the baseline values and $\geq 3 \times$ ULN, or $\geq 8 \times$ ULN (whichever is smaller).
 - ii. For patients with pre-existing values of total bilirubin above the normal range: Total bilirubin increased by one time the upper limit of normal or ≥ 3 times the upper limit of normal (whichever is smaller).

D. Myelosuppression (Anemia, Neutropenia, Leukopenia) considered clinically significant by the investigator.

E. Hemorrhage considered clinically significant by the investigator

F. Infection

G. Skin disorders (Rash) considered clinically significant by the investigator

H. Clinically significant immunological events (Hypersensitivity)

I. Renal dysfunction (increased blood creatinine considered clinically significant by the investigator)

J. Pleural effusions

K. Clinically significant cardiac events (QT prolongation, atrial fibrillation, sinus bradycardia, tachycardia, supraventricular tachycardia, bradycardia, premature ventricular contractions, pericardial effusion, right bundle branch block, sinus tachycardia, or premature atrial contractions).

2) In relation to atezolizumab:

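### A DLT that is neither an SAE nor an AESI has no deadline for reaching the sponsor, so the Group 1 stopping count can lag

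*Protocol*

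**What the plan says.** Protocol section 9.3.1 (repeated in SAP 4.1) states the Group 1 rule: "If dose-limiting toxicities (DLTs) appear in 2 or more patients the study will end". Among the DLT criteria, for events at least possibly related to either drug, is "Any Grade 3 or 4 clinically evident non-hematological toxicity". It carries no minimum duration and no seriousness condition.

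Section 13.4 defines the expedited route: "The investigator shall report all SAEs and AESIs to FTH", within 24 hours of the investigator learning of the event. Section 13.9.1 fixes which events are AESIs: "The sponsor has determined that the events listed below (whether considered serious or non-serious by investigators) should be considered AESIs". The bosutinib and atezolizumab lists that follow include neither fatigue nor asthenia, and neither list names DLTs as a class.

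All other adverse events go to the eCRF (13.4). Section 18.4 asks that entry be timely but gives no number of days. The Synopsis allows up to 10 centers.

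**The concern.** The stopping rule counts patients across sites, so only someone who pools the sites' reports can know that the second DLT has occurred. The written reporting rule does not ensure that this person hears of every DLT promptly. A site that complies fully can leave the sponsor unaware of a DLT for an unspecified time. During that time other Group 1 patients, on infusions every 2 weeks, can be given more of a combination whose trial should already have ended.

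**Working it through.** **Step 1: follow one event through the protocol.** Take a related Grade 3 fatigue that the investigator judges non-serious and that resolves within 7 days of the last infusion.

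| Provision | Result for this event |
|---|---|
| 9.3.1, DLT criteria | Counts as a DLT |
| 13.8, SAE criteria | Not an SAE, by investigator judgement |
| 13.9.1, both AESI lists | Not listed |
| 11.6.2, atezolizumab | Exempt from withholding: "Grade 3 fatigue that was present at baseline or that lasts for <7 days after the last administration of atezolizumab"; the asthenia exemption is worded the same way |
| 11.6.1.1, Table 1, general Grade 3 row | Applies to persistent toxicity, defined in footnote b as "symptoms of toxicity which, despite optimal medical management, persist for ≥ 14 days"; sponsor contact only if recovery takes more than 4 weeks |
| 11.6.1.1, text below Table 1 | Withholds bosutinib for Grade 3 toxicity that does not respond to optimal management, without repeating the 14 days; asks for no sponsor contact |
| 13.4 and 18.4 | eCRF entry, no stated limit |
| 16, medical monitor review | No stated timing |
| 18.3, full source verification | Covers consent, eligibility and SAE documentation, not DLTs |

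The example is realistic: section 6.3 names fatigue among the most common severe adverse events of atezolizumab.

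**Step 2: other DLTs.** Many already have the 24-hour clock: Grade 3-4 diarrhea, nausea and vomiting, any infection, and several events judged clinically significant (13.9.1). Grade 4 bosutinib toxicity (Tables 1 and 2) and several Grade 3 immune-mediated events (for example pulmonary and hepatic, Tables 3 and 4) call for sponsor review or contact, but with no deadline.

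**Step 3: size.** The plan has no figure for reporting lag, so there is none to reproduce. The inputs are:

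- Table 14 schedules 840 mg infusions on D29, D43, D57 and D71. That is 4 per patient and 4 × 10 = 40 in Group 1.
- Nominal spacing is 14 days, so n patients in the window receive about n × L/14 infusions in a lag of L days.
- L is assumed. So is n: 8 if all ten are in the window and both DLT patients are held, 10 if neither is held (which the fatigue exemption allows).

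| Assumed lag L | n = 8 | n = 10 |
|---|---|---|
| 14 days | 8 × 14/14 = 8 (8/40 = 20%) | 10 × 14/14 = 10 (10/40 = 25%) |
| 7 days, infusion days evenly spread | 8 × 7/14 = 4 | 10 × 7/14 = 5 |
| 1 day (24-hour report) | 8/14 = 0.57 | 10/14 = 0.71 |

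Fewer patients in the window scale these down, to 0 when no one is due an infusion.

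**Step 4: could the threshold be reached?** The true DLT rate p is not given. P(2 or more of 10) = 1 − (1−p)^10 − 10p(1−p)^9. This is 0.264 at an assumed p of 10% and 0.624 at 20%, so crossing the threshold is not remote.

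**The case against.** The strongest reply is that little is left uncovered. Most severe toxicities expected with these drugs are AESIs or would be serious. An investigator can also treat disabling fatigue as serious under the incapacity or significant-medical-event criteria in 13.8. That is true, but it rests on judgement, and 13.9.1 itself provides for Grade 3-4 events that investigators consider non-serious.

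Second, the example is an event the protocol thinks mild enough to keep dosing the same patient, and other patients remain protected by their own toxicity rules. This limits the clinical harm. It does not change the event's status as one of the two that end the study.

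Third, section 9.1 frames the rule as at least 9 of 10 patients free of DLTs during the first 2 combination cycles, which can be read as an assessment at the end of the window. On that reading a mid-window lag matters little. Section 9.3.1 says the study ends if DLTs appear in 2 or more patients and does not say to wait, so both readings are open.

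Fourth, the upper figure is a worst case. Planned enrollment is 36 patients in 12 months, or 3 a month. If entry were even at that pace (an assumption), about 3 × 56/30.4 = 5.5 patients would be in an 8-week window together, not 10. This objection stands.

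Fifth, a Reference Manual (13.5) and a monitoring plan (16.2, 18.3) exist but are not among the documents. They are cited for severity grading and for monitoring scope, and the protocol does not say that either sets a DLT reporting time. One might.

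**Conclusion.** The gap is real but limited. The 24-hour route is narrower than the DLT definition, and the stopping rule depends on a pooled count. The effect is delay in a subset of DLTs. The number of extra infusions cannot be derived from the documents. It is 0 if no one is due, about n × L/14 otherwise, and 8 to 10 only as a ceiling that needs an assumed 14-day lag with all ten patients in the window together. It also assumes that the rule is meant to act as soon as the second DLT occurs, and that one of the first two DLTs falls outside the SAE and AESI definitions.

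A reader might infer more, and the documents do not support it:

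- **DLTs are lost and Group 2 opens in error.** The events are still recorded on the eCRF, and opening Group 2 requires at least 9 of 10 patients without a DLT, which is a positive checkpoint.
- **The same harm arises from the 1680 mg trigger in 9.3.2.** That rule changes the regimen to 840 mg every 2 weeks, and 2 × 840 = 1680 mg per 4 weeks, so a late trigger adds no dose.
- **8 to 10 is the expected number of infusions.** It is the ceiling only.

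**What to change.** In Protocol 13.4 and 13.9.1, make any suspected DLT during combination therapy reportable to the sponsor within 24 hours on the existing SAE/AESI form. The simplest way is to list DLT as an AESI. If the study manual already contains such a step, cite it in 13.4 instead.

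The protocol already gives a 24-hour clock to pregnancy (13.14) and to overdose and medication error, even without an adverse event (13.15), so the mechanism exists. The cost is a line of wording and a tick-box on the form. The downside is a few more expedited reports from sites. No new visit or committee is needed.

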13.5 AE Severity

The severity of AEs will be assessed according to the NCI CTCAE, v5.0 (see Appendix C and the study Reference Manual). If the AE is not defined in the CTCAE, the investigator will determine its severity based on the following definitions:

- *Mild (grade 1)*: The AE is noticeable to the patient but does not interfere with routine activity.
- *Moderate (grade 2)*: The AE interferes with routine activity but responds to symptomatic therapy.
- *Severe (grade 3)*: The AE significantly limits the patient's ability to perform routine activities despite symptomatic therapy.
- *Life-threatening (grade 4)*: The patient is at immediate risk of death.
- *Death (grade 5)*: The patient dies as a direct result of the complication or condition induced by the AE.

13.6 Causality

The investigator's assessment of causality must be provided for all AEs (serious and non-serious). An investigator's causality assessment is the determination of whether there is a reasonable possibility that the investigational product caused or contributed to the AE.

In addition, if the investigator determines that a SAE is associated with study procedures, the investigator must record this causal relationship in the source documents and on the SAE form. The investigator must report such assessment in accordance with the SAE reporting requirements.

The investigator will use both medical consideration and the following categories of causality to determine the causal relationship of an AE to the study drug (based on the definitions below). Not all criteria in each category of relatedness must be present.

Definitely Not Related (Not Drug-Related)

- The patient did not receive study drug, or
- The temporal sequence of the AE onset, relative to the administration of study drug, is not reasonable, or
- There is another obvious cause for the AE

Probably Not Related (Not Drug-Related)

There is evidence of exposure to study drug and one of the following:

- There is another, more likely cause of the AE
- Dechallenge (if performed) is negative or ambiguous
- Rechallenge (if performed) is negative or ambiguous

Possibly Related (Drug-Related)

There is evidence of exposure to study drug and one of the following:

- The temporal sequence of the AE onset, relative to administration of study drug, is reasonable
- The AE could have been due to another equally likely cause
- Dechallenge (if performed) is positive

Probably Related (Drug-Related)

There is evidence of exposure to study drug and one of the following:

- The temporal sequence of the AE onset, relative to administration of study drug, is reasonable
- The AE is more likely explained by study drug than by another cause

Definitely Related (Drug Related)

There is evidence of exposure to study drug and one of the following:

- The temporal sequence of the AE onset, relative to administration of study drug, is reasonable
- Dechallenge is positive
- The AE shows a pattern consistent with previous knowledge of the test drug or a test drug class

13.7 Expectedness

The current Clinical Investigator's Brochures (CIB) will be used as the reference for determination of expectedness and risk assessment for bosutinib and atezolizumab.

13.8 SAEs

The definitions and reporting requirements of ICH Guidelines for Clinical Safety Data Management, Definitions and Standards for Expedited Reporting, Topic E2A, as well as the Royal Decree 1090/2015, of 4 December, regulating clinical trials with medicinal products, Ethics Committees for Investigation with medicinal products and the Spanish Clinical Studies Registry will be followed.

The investigator or sponsor may determine the seriousness of an AE based on the following. An AE is considered a SAE if at least one of these conditions applies:

- *Death:* if the death occurs within the time of the first dose and the 28 days after the last dose and the cause of death is the event.
- *Life-threatening:* An AE that places the patient, in the view of the investigator or the sponsor, at immediate risk of death from the event as it occurred (e.g., this does not include an event that, had it occurred in a more severe form, might have caused death)
- Results in a persistent or significant incapacity or substantial disruption of the ability to conduct normal life functions
- *Inpatient hospitalization or prolongation of existing hospitalization:* Hospitalization refers to admission of a patient into a hospital for any length of time.
- *A congenital anomaly/birth defect:* A fixed, permanent impairment established at or before birth

- Is a significant medical event in the investigator's judgment (e.g., may jeopardize the patient or may require medical/surgical intervention to prevent one of the outcomes listed above)

Events that are clearly consistent with the expected pattern of progression of the underlying disease should not be recorded as serious adverse events SAES.

13.9 Adverse Event of Special Interest (AESI) Definition

Medical and scientific judgment should be exercised in determining whether an event is an important medical event. An important medical event may not result in death, be life-threatening, or require hospitalization. However, if it is determined that the event may jeopardize the patient and/or may require intervention to prevent one of the other outcomes listed in the definition above, that important medical event should be reported as serious. Examples of such events are intensive treatment in an emergency room or at home for allergic bronchospasm, blood dyscrasias, or convulsions that do not result in hospitalization, or the development of drug dependency or drug abuse.

13.9.1 Adverse Event of Special Interest

AESIs require ongoing monitoring by investigators and rapid identification and communication by the investigator to the sponsor. All AESIs, whether they are SAEs or not, must be reported immediately (within 24 hours) to the sponsor. The sponsor has determined that the events listed below (whether considered serious or non-serious by investigators) should be considered AESIs, and should therefore be reported within 24 hours:

- 1) In relation to bosutinib:
 - A. Grade 3-4 diarrhea
 - B. Grade 3-4 nausea and vomiting
 - C. Potential drug-induced liver injury showed by abnormal values in liver enzyme (ALT increased and AST increased) concurrent with abnormal elevation in total bilirubin that meet the criteria outlined below:
 - a. Patients with AST or ALT and total bilirubin baseline values within the normal range who subsequently present with AST or ALT ≥ 3 times the upper limit of normal concurrent with a total bilirubin $\geq 2 \times$ ULN with no evidence of hemolysis and an alkaline phosphatase $\leq 2 \times$ ULN or not available;
 - b. For patients with preexisting ALT or AST or total bilirubin values above the upper limit of normal, the following threshold values should be used:
 - i. For patients with pre-existing AST or ALT baseline values above the normal range: AST or ALT ≥ 2 times the baseline values and $\geq 3 \times$ ULN, or $\geq 8 \times$ ULN (whichever is smaller).
 - ii. For patients with pre-existing values of total bilirubin above the normal range: Total bilirubin increased by one time the upper limit of normal or ≥ 3 times the upper limit of normal (whichever is smaller).

D. Myelosuppression (Anemia, Neutropenia, Leukopenia) considered clinically significant by the investigator.

E. Hemorrhage considered clinically significant by the investigator

F. Infection

G. Skin disorders (Rash) considered clinically significant by the investigator

H. Clinically significant immunological events (Hypersensitivity)

I. Renal dysfunction (increased blood creatinine considered clinically significant by the investigator)

J. Pleural effusions

K. Clinically significant cardiac events (QT prolongation, atrial fibrillation, sinus bradycardia, tachycardia, supraventricular tachycardia, bradycardia, premature ventricular contractions, pericardial effusion, right bundle branch block, sinus tachycardia, or premature atrial contractions).

2) In relation to atezolizumab:

- A. Cases of potential drug-induced liver injury that include an elevated ALT or AST in combination with either an elevated bilirubin or clinical jaundice, as defined by Hy's Law (see *EASL, 2019*)
- B. Suspected transmission of an infectious agent by the study treatment, as defined below
 - Any organism, virus, or infectious particle (e.g., prion protein transmitting transmissible spongiform encephalopathy), pathogenic or non-pathogenic, is considered an infectious agent. A transmission of an infectious agent may be suspected from clinical symptoms or laboratory findings that indicate an infection in a patient exposed to a medicinal product. This term applies only when a contamination of study treatment is suspected.

C. Systemic lupus erythematosus

D. Events suggestive of hypersensitivity, infusion-related reactions, cytokine-release syndrome, macrophage activating syndrome, hemophagocytic lymphohistiocytosis

E. Nephritis

F. Ocular toxicities (e.g., uveitis, retinitis, optic neuritis)

G. Grade ≥ 2 cardiac disorders (e.g., atrial fibrillation, myocarditis, pericarditis)

H. Vasculitis

I. Autoimmune hemolytic anemia

J. Severe cutaneous reactions (e.g., Stevens-Johnson syndrome, dermatitis bullous, toxic epidermal necrolysis)

